5.3.5.6. Management of Avelumab-Related Severe Hypersensitivity Reactions and Flu-Like Symptoms

As with all monoclonal antibody therapies, avelumab can induce flu-like symptoms and hypersensitivity reactions, including impaired airway, decreased oxygen saturation (<92%), confusion, lethargy, hypotension, pale/clammy skin, and cyanosis.

Avelumab should be administered in a setting that allows for immediate access to an intensive care unit or equivalent environment if required. Patient should be placed on monitor immediately and epinephrine injection and dexamethasone infusion should be available for immediate access.

090177e1907c3de010.1\Draft\Versioned On:01-Mar-2019 17:22 (GMT)

[figure not shown]
For prophylaxis of flu-like symptoms, 25 mg indomethacin or comparable non-steroidal anti-inflammatory drug (NSAID) dose (eg, ibuprofen 600 mg, naproxen sodium 500 mg) may be administered at investigator discretion 2 hours before and 8 hours after the start of each dose of avelumab IV infusion. Alternative treatments for fever (eg, paracetamol or ibuprofen) and rigors (eg, meperidine) may be given to patients at the discretion of the investigator.

Additional treatment recommendations for symptoms of avelumab infusion-related reactions are provided in [Appendix 6](#) and may be modified based on local treatment standards and guidelines, as appropriate.

5.3.5.7. Management of Avelumab-Related Tumor Lysis Syndrome

Avelumab can induce antibody-dependent cell-mediated cytotoxicity (ADCC), so there is a potential risk of tumor lysis syndrome (TLS). Should this occur, patients should be treated as per local guidelines and the management algorithm ([Figure 1](#)) published by Howard et al.³⁵

Figure 1. Assessment and Initial Management of Tumor Lysis Syndrome

090177e1907c3de0\0.1\Draft\Versioned On:01-Mar-2019 17:22 (GMT)

5.3.5.8. Management of Avelumab Immune-Related Adverse Events

Since inhibition of PD-L1 stimulates the immune system, irAEs may occur. Treatment of irAEs is mainly dependent upon severity (NCI CTCAE grade v. 4.03):

- Grade 1 to 2: treat symptomatically or with moderate-dose steroids, more frequent monitoring;
- Grade 1 to 2 (persistent): manage similar to Grade 3 to 4 AE;
- Grade 3 to 4: treat with high-dose corticosteroids.

Treatment of irAEs should follow guidelines set forth in Table 7.

Some potential irAEs described with anti-PD-L1 drugs such as avelumab may overlap with axitinib toxicities (eg, diarrhea, elevated liver function tests). Any adverse event suspected to be immune-related should be managed according to the guidance for management of irAEs in this section.

For potential overlapping Grade 2 irAEs, hold both drugs used in the combination (avelumab and axitinib) and follow the specific management recommendations described in Table 7. When the event resolves to Grade ≤ 1 , restart therapy with axitinib. If the Grade ≥ 2 event does not recur, restart avelumab at the beginning of the next treatment cycle. If the Grade ≥ 2 event does not resolve to Grade ≤ 1 after holding avelumab for 2 treatment cycles (up to 28 days) or if the Grade ≥ 2 event recurs after re-introduction of avelumab, permanently discontinue avelumab therapy.

For potential overlapping Grade ≥ 3 irAEs, hold axitinib and follow the specific guidance in Table 7 for avelumab. When the event resolves to Grade ≤ 1 , restart therapy with axitinib at reduced dose level. Avelumab should be permanently discontinued.

Table 7. Management of Avelumab Immune Related Adverse Events

Gastrointestinal irAEs		
Severity of Diarrhea / Colitis (NCI CTCAE v4)	Initial Management	Follow-up Management
Grade 1 Diarrhea: <4 stools/day over baseline; Colitis: asymptomatic	Continue avelumab therapy Symptomatic treatment (eg. loperamide).	Close monitoring for worsening symptoms. Educate patient to report worsening immediately. If worsens: Treat as Grade 2, 3 or 4.
Grade 2 Diarrhea: 4 to 6 stools per day over baseline; IV fluids indicated <24 hours; not interfering with ADL Colitis: abdominal pain; blood in	Withhold avelumab therapy Symptomatic treatment.	If improves to Grade ≤ 1 : Resume avelumab therapy If persists >5-7 days or recurs: Treat as Grade 3 or 4.

090177e1907c3de0\0.1\Draft\Versioned On:01-Mar-2019 17:22 (GMT)

stool		
Grade 3 to 4 Diarrhea (Grade 3): ≥ 7 stools per day over baseline; incontinence; IV fluids ≥ 24 hrs; interfering with ADL Colitis (Grade 3): severe abdominal pain, medical intervention indicated, peritoneal signs Grade 4: life-threatening, perforation	Withhold avelumab for Grade 3. Permanently discontinue avelumab for Grade 4 or recurrent Grade 3. 1.0 to 2.0 mg/kg/day prednisone IV or equivalent. Add prophylactic antibiotics for opportunistic infections. Consider lower endoscopy.	If improves: Continue steroids until Grade ≤ 1 , then taper over at least 1 month; resume avelumab therapy following steroids taper (for initial Grade 3). If worsens, persists >3 to 5 days, or recurs after improvement: Add infliximab 5mg/kg (if no contraindication). Note: infliximab should not be used in cases of perforation or sepsis.
Dermatological irAEs		
Grade of Rash (NCI-CTCAE v4)	Initial Management	Follow-up Management
Grade 1 to 2 Covering $\leq 30\%$ body surface area	Continue avelumab therapy. Symptomatic therapy (for example, antihistamines, topical steroids).	If persists >1 to 2 weeks or recurs: Withhold avelumab therapy. Consider skin biopsy. Consider 0.5-1.0 mg/kg/day prednisone or equivalent. Once improving, taper steroids over at least 1 month, consider prophylactic antibiotics for opportunistic infections, and resume avelumab therapy following steroids taper. If worsens: Treat as Grade 3 to 4.
Grade 3 to 4 Grade 3: Covering $>30\%$ body surface area; Grade 4: Life threatening consequences	Withhold avelumab for Grade 3. Permanently discontinue for Grade 4 or recurrent Grade 3. Consider skin biopsy. Dermatology consult 1.0 to 2.0 mg/kg/day prednisone or equivalent. Add prophylactic antibiotics for opportunistic infections.	If improves to Grade ≤ 1 : Taper steroids over at least 1 month; resume avelumab therapy following steroids taper (for initial Grade 3).
Pulmonary irAEs		
Grade of Pneumonitis (NCI-CTCAE v4)	Initial Management	Follow-up Management
Grade 1 Radiographic changes only	Consider withholding avelumab therapy. Monitor for symptoms every 2 to 3 days.	Re-assess at least every 3 weeks If worsens: Treat as Grade 2 or Grade 3 to 4.

090177e1907c3de0\0.1\Draft\Versioned On:01-Mar-2019 17:22 (GMT)

	Consider Pulmonary and Infectious Disease consults.	
Grade 2 Mild to moderate new symptoms	Withhold avelumab therapy Pulmonary and Infectious Disease consults. Monitor symptoms daily; consider hospitalization 1.0 to 2.0 mg/kg/day prednisone or equivalent. Add prophylactic antibiotics for opportunistic infections. Consider bronchoscopy, lung Biopsy.	Re-assess every 1 to 3 days If improves: When symptoms return to Grade ≤ 1 , taper steroids over at least 1 month, and then resume avelumab therapy following steroids taper If not improving after 2 weeks or worsening: Treat as Grade 3 to 4.
Grade 3 to 4 Grade 3: Severe new symptoms; New/worsening hypoxia; Grade 4: Life-threatening	Permanently discontinue avelumab therapy. Hospitalize. Pulmonary and Infectious Disease consults. 1.0 to 2.0 mg/kg/day prednisone or equivalent. Add prophylactic antibiotics for opportunistic infections. Consider bronchoscopy, lung Biopsy.	If improves to Grade ≤ 1 : Taper steroids over at least 1 month If not improving after 48 hours or worsening: Add additional immunosuppression (for example, infliximab, cyclophosphamide, IV immunoglobulin, or mycophenolate mofetil).
Hepatic irAEs		
Grade of Liver Test Elevation (NCI-CTCAE v4)	Initial Management	Follow-up Management
Grade 1 Grade 1 AST or ALT > ULN to 3.0 x ULN and/or Total bilirubin > ULN to 1.5 x ULN	Continue avelumab therapy.	Continue liver function monitoring If worsens: Treat as Grade 2 or 3 to 4.
Grade 2 AST or ALT >3.0 to ≤ 5 x ULN and/or total bilirubin >1.5 to ≤ 3 x ULN	Withhold avelumab therapy Increase frequency of monitoring to every 3 days.	If returns to Grade ≤ 1 : Resume routine monitoring; resume avelumab therapy. If elevation persists >5 to 7 days or worsens: Treat as Grade 3 to 4.
Grade 3 to 4 AST or ALT >5 x ULN and /or total bilirubin >3 x ULN	Permanently discontinue avelumab therapy. Increase frequency of monitoring to every 1 to 2 days. 1.0 to 2.0 mg/kg/day prednisone or equivalent.	If returns to Grade ≤ 1 : Taper steroids over at least 1 month. If does not improve in >3 to 5 days, worsens or rebounds: Add mycophenolate mofetil 1 gram (g) twice daily. If no response within an additional 3

090177e1907c3de0\0.1\Draft\Versioned On:01-Mar-2019 17:22 (GMT)

	Add prophylactic antibiotics for opportunistic infections. Consult gastroenterologist/ Hepatologist. Consider obtaining MRI/CT scan of liver and liver biopsy if clinically warranted.	to 5 days, consider other immunosuppressants per local guidelines.
Renal irAEs		
Grade of Creatinine Increased (NCI-CTCAE v4)	Initial Management	Follow-up Management
Grade 1 Creatinine increased > ULN to 1.5 x ULN	Continue avelumab therapy.	Continue renal function monitoring. If worsens: Treat as Grade 2 to 3 or 4.
Grade 2 to 3 Creatinine increased >1.5 and ≤6 x ULN	Withhold avelumab therapy. Increase frequency of monitoring to every 3 days. 1.0 to 2.0 mg/kg/day prednisone or equivalent. Add prophylactic antibiotics for opportunistic infections. Consider renal biopsy.	If returns to Grade ≤1: Taper steroids over at least 1 month, and resume avelumab therapy following steroids taper. If worsens: Treat as Grade 4.
Grade 4 Creatinine increased > 6 x ULN	Permanently discontinue avelumab therapy. Monitor creatinine daily 1.0 to 2.0 mg/kg/day prednisone or equivalent. Add prophylactic antibiotics for opportunistic infections. Consider renal biopsy. Nephrology consult.	If returns to Grade ≤1: Taper steroids over at least 1 month.
Cardiac irAEs		
Myocarditis	Initial Management	Follow-up Management
New onset of cardiac signs or symptoms and / or new laboratory cardiac biomarker elevations (eg, troponin, CK-MB, BNP) or cardiac imaging abnormalities suggestive of myocarditis.	Withhold avelumab therapy. Hospitalize. In the presence of life threatening cardiac decompensation, consider transfer to a facility experienced in advanced heart failure and arrhythmia management. Cardiology consult to establish etiology and rule-out immune-mediated myocarditis. Guideline based supportive treatment as per cardiology consult.* Consider myocardial biopsy if recommended per cardiology consult.	If symptoms improve and immune-mediated etiology is ruled out, re-start avelumab therapy. If symptoms do not improve/worsen, viral myocarditis is excluded, and immune-mediated etiology is suspected or confirmed following cardiology consult, manage as immune-mediated myocarditis.

090177e1907c3de0\0.1\Draft\Versioned On:01-Mar-2019 17:22 (GMT)

Immune-mediated myocarditis	Permanently discontinue avelumab. Guideline based supportive treatment as appropriate as per cardiology consult.* 1.0 to 2.0 mg/kg/day prednisone or equivalent. Add prophylactic antibiotics for opportunistic infections.	Once improving, taper steroids over at least 1 month. If no improvement or worsening, consider additional immunosuppressants (eg, azathioprine, cyclosporine A).

*Local guidelines, or eg. ESC or AHA guidelines ESC guidelines website: https://www.escardio.org/Guidelines/Clinical-Practice-Guidelines AHA guidelines website: http://professional.heart.org/professional/GuidelinesStatements/searchresults.jsp?q=&y=&t=1001
		
Endocrine irAEs		
Endocrine Disorder	Initial Management	Follow-up Management
Grade 1 or Grade 2 Endocrinopathies (hypothyroidism, hyperthyroidism, adrenal insufficiency, type I diabetes mellitus)	Continue avelumab therapy Endocrinology consult if needed Start thyroid hormone replacement therapy (for hypothyroidism), anti-thyroid treatment (for hyperthyroidism), corticosteroids (for adrenal insufficiency) or insulin (for Type I diabetes mellitus) as appropriate. Rule-out secondary endocrinopathies (ie, hypopituitarism / hypophysitis).	Continue hormone replacement/suppression and monitoring of endocrine function as appropriate.
Grade 3 or Grade 4 endocrinopathies (hypothyroidism, hyperthyroidism, adrenal insufficiency, type I diabetes mellitus)	Withhold avelumab therapy. Consider hospitalization. Endocrinology consult. Start thyroid hormone replacement therapy (for hypothyroidism), anti-thyroid treatment (for hyperthyroidism), corticosteroids (for adrenal insufficiency) or insulin (for type I diabetes mellitus) as appropriate. Rule-out secondary endocrinopathies (ie, hypopituitarism/hypophysitis).	Resume avelumab once symptoms and/or laboratory tests improve to Grade ≤ 1 (with or without hormone replacement/suppression). Continue hormone replacement/suppression and monitoring of endocrine function as appropriate.
Hypopituitarism/Hypophysitis (secondary endocrinopathies)	If secondary thyroid and/or adrenal insufficiency is confirmed (ie, subnormal serum FT4 with inappropriately low TSH and/or low serum cortisol with inappropriately low ACTH):	Resume avelumab once symptoms and hormone tests improve to Grade ≤ 1 (with or without hormone replacement). In addition, for hypophysitis with abnormal MRI, resume avelumab only once shrinkage of the pituitary

090177e1907c3de0\0.1\Draft\Versioned On:01-Mar-2019 17:22 (GMT)

	
 - Refer to endocrinologist for dynamic testing as indicated and measurement of other hormones (FSH, LH, GH/IGF-1, PRL, testosterone in men, estrogens in women). - Hormone replacement/suppressive therapy as appropriate. - Perform pituitary MRI and visual field examination as indicated. 
If hypophysitis confirmed:
 
 - Continue avelumab if mild symptoms with normal MRI. Repeat the MRI in 1 month - - Withhold avelumab if moderate, severe or life-threatening symptoms of hypophysitis and/or abnormal MRI. Consider hospitalization. Initiate corticosteroids (1 to 2 mg/kg/day prednisone or equivalent) followed by corticosteroids taper during at least 1 month. - Add prophylactic antibiotics for opportunistic infections. 	
gland on MRI/CT scan is documented.
 
Continue hormone replacement/suppression therapy as appropriate.

Other irAEs (not described above)		
Grade of other irAEs (NCI-CTCAE v4)	Initial Management	Follow-up Management
Grade 2 or Grade 3 clinical signs or symptoms suggestive of a potential irAE	Withhold avelumab therapy pending clinical investigation.	If irAE is ruled out, manage as appropriate according to the diagnosis and consider re-starting avelumab therapy. If irAE is confirmed, treat as Grade 2 or 3 irAE.
Grade 2 irAE or first occurrence of Grade 3 irAE	Withhold avelumab therapy 1.0 to 2.0 mg/kg/day prednisone or equivalent. Add prophylactic antibiotics for opportunistic infections. Specialty consult as appropriate.	If improves to Grade \leq 1: Taper steroids over at least 1 month and resume avelumab therapy following steroids taper.
Recurrence of same Grade 3 irAEs	Permanently discontinue avelumab therapy 1.0 to 2.0 mg/kg/day prednisone or equivalent. Add prophylactic antibiotics for opportunistic infections. Specialty consult as appropriate	If improves to Grade \leq 1: Taper steroids over at least 1 month.

090177e1907c3de0\0.1\Draft\Versioned On:01-Mar-2019 17:22 (GMT)

Grade 4	Permanently discontinue avelumab Therapy 1.0 to 2.0 mg/kg/day prednisone or equivalent and/or other immunosuppressant as needed. Add prophylactic antibiotics for opportunistic infections. Specialty consult.	If improves to Grade \leq 1: Taper steroids over at least 1 month.
Requirement for 10 mg per day or greater prednisone or equivalent for more than 12 weeks for reasons other than hormonal replacement for adrenal insufficiency Persistent Grade 2 or 3 irAE lasting 12 weeks or longer	Permanently discontinue avelumab therapy. Specialty consult.	

Abbreviations: ACTH=adrenocorticotropic hormone; ADL=activities of daily living; ALT=alanine aminotransferase; AST=aspartate aminotransferase; BNP=B-type natriuretic peptide; CK-MB=creatine kinase MB; CT= computed tomography; FSH=follicle-stimulating hormone; GH=growth hormone; IGF-1=insulin-like growth factor 1; irAE=immune-related adverse event; IV=intravenous; LH=luteinizing hormone; MRI=magnetic resonance imaging; NCI-CTCAE=National Cancer Institute-Common Terminology Criteria for Adverse Events; PRL=prolactin; T4=thyroxine; TSH=thyroid-stimulating hormone; ULN=upper limit of normal.

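### Protocol 5.3.5.8 and its Table 7 give opposite avelumab instructions for Grade 2 hypothyroidism and for Grade 2 liver-test elevation that outlasts 5–7 days but resolves by day 28

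*Protocol*

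**What the plan says.** Section 5.3.5.8 opens with a general pointer, "Treatment of irAEs should follow guidelines set forth in Table 7", and a short list by grade. In that list, a Grade 1–2 event that persists is to be handled like a Grade 3–4 event.

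The section then sets separate rules for immune-related events that may overlap with axitinib toxicity, giving diarrhea and raised liver tests as examples. The Grade 2 rule begins: for "overlapping Grade 2 irAEs, hold both drugs used in the combination (avelumab and axitinib) and follow the specific management recommendations described in Table 7". Axitinib restarts once the event is Grade 1 or below. If it does not recur, the site is to "restart avelumab at the beginning of the next treatment cycle". Avelumab is stopped for good if the event has not come down to that level "after holding avelumab for 2 treatment cycles (up to 28 days", or if it recurs after re-introduction.

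Table 7 has its own organ-specific rows:

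- Endocrine, Grade 1 or 2 (hypothyroidism is listed): "Continue avelumab therapy Endocrinology consult if needed", with thyroid hormone replacement and no time limit.
- Hepatic, Grade 2: withhold, retest every 3 days and resume on return to Grade 1 or below, but "If elevation persists >5 to 7 days or worsens: Treat as Grade 3 to 4".
- Hepatic, Grade 3 to 4: "Permanently discontinue avelumab therapy. Increase frequency of monitoring to every 1 to 2 days".

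**The concern.** The Grade 2 paragraph orders a hold and, in the same sentence, sends the site to a table that may say something else. For two events a site cannot obey both texts, and nothing states which one governs.

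What is at stake is consistent patient management. A site that follows the paragraph would withhold avelumab, and might eventually stop it, for hypothyroidism that Table 7 manages with hormone replacement while avelumab continues. For the same liver-test elevation, one site could restart avelumab while another had already discontinued it permanently, and each would be complying with the protocol.

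**Working it through.** **1. Are the two events in scope?** Raised liver tests are one of the section's own examples of overlap. Hypothyroidism is not among those examples, but they are introduced as examples only. The Protocol Summary, Section 1.2.3 and Section 1.3 each name hypothyroidism as an expected overlapping toxicity.

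**2. The plan's own figure.** The Schedule of Activities sets a 14-day cycle, so 2 cycles × 14 days = 28 days, as stated. With dosing every 2 weeks, 28 / 14 = 2 avelumab doses.

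**3. Grade 2 hypothyroidism.**

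- Paragraph: hold from onset, up to 2 doses withheld, then a permanent stop if not Grade 1 or below.
- Table 7: continue, 0 doses withheld, no stop rule in that row.

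The conflict exists from the first day. For comparison, Table 7 allows avelumab to resume even after Grade 3 or 4 endocrinopathy once it improves to Grade 1 or below.

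**4. Grade 2 liver-test elevation.** Assume that both clocks start on the same day and that the event neither worsens nor recurs. Apply each rule to the day of resolution:

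| Day of resolution | Grade 2 paragraph | Table 7 | Same outcome? |
|---|---|---|---|
| 1–5 | restart | resume | yes |
| 6–7 | restart | depends on where in the 5-to-7-day range the limit is set | unclear |
| 8–28 | restart | permanently stopped | no |
| after 28 | permanently stopped | permanently stopped | yes |

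With the 7-day limit the rules disagree on 28 − 8 + 1 = 21 days. With the 5-day limit they disagree on 28 − 6 + 1 = 23 days. These are calendar days. They do not count decisions or patients, because Table 7 retests every 3 days and the paragraph restarts only at a cycle start.

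**5. Does any text rank the two?**

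- The general pointer favors Table 7, but it comes before the overlap rules and does not mention a conflict.
- The sentence that sends the reader to Table 7 also orders the hold, and the paragraph goes on to set its own restart and stop rules.
- For avelumab in immune-related events, Table 5 cites Section 5.3.5.8 and Table 7 together, unranked.
- The next paragraph, on Grade 3 and above, also cites Table 7 and then stops avelumab permanently, although Table 7 allows resumption after a first Grade 3 diarrhea. So a reader cannot assume that Table 7 always prevails.

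For liver tests alone, the opening list's treatment of persistent Grade 1–2 events agrees with Table 7's escalation. That suggests which text is meant to win there, but it does not cancel the restart instruction.

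**The case against.** **Hypothyroidism is brought in by inference.** It comes from background sections, which do not define the scope of 5.3.5.8. This stands as a caution. But the section's list is illustrative, and three places in the protocol name hypothyroidism as an expected overlap, so a site would have good reason to apply the paragraph.

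**The 28 days can be read as an outer limit.** On that reading Table 7 acts first for liver tests, with support from the persistent-event bullet. The reading is sensible and the fix adopts it. No text states it, however, and it does nothing for hypothyroidism.

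**The medical monitor would catch it.** Section 5.3.5.3 asks for discussion of any modification or discontinuation for persistent toxicity, and for consultation before a patient is discontinued. This stands for permanent stops in both cases, including hypothyroidism unresolved at 28 days. It protects the initial decision less well, because for Grades 1 and 2 sites need only consider consulting.

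**Stronger readings that the documents do not support.**

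- A reader might see a further conflict between 28 days and Table 7's 12-week rule ("Persistent Grade 2 or 3 irAE lasting 12 weeks or longer"). That row sits under irAEs not described elsewhere in the table. A specific and a general limit can coexist, and no event has been shown to fall under both.
- A reader might conclude that Table 7 should simply override the paragraph. For Grade 2 diarrhea, Table 7 escalates persistence to Grade 3–4 management, in which a first Grade 3 event may resume after a steroid taper. A blanket override would therefore remove the 28-day stop for a named overlap, in a combination with no prior patient safety data.
- A reader might infer an axitinib conflict. Table 5 and the paragraph both hold axitinib for Grade 2, so there is none.

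**Conclusion.** The contradiction is real and narrow. For Grade 2 hypothyroidism the instructions differ from onset: 0 doses withheld against up to 2, with a permanent stop possible under one text only. For Grade 2 liver tests the outcomes are opposite when resolution falls on about days 8 to 28 (21 days, or 23 counting from day 6). This rests on hypothyroidism counting as an overlapping event and, for liver tests, on a common starting day. The documents give no rate of either event on the combination, so no patient number follows.

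A reader might infer that DLT counts or the RP2D were affected. Section 3.1.2 counts failure to complete 2 infusions because of drug-related toxicity as a DLT, and Section 3.4 weighs discontinuations for immune-related toxicity. The documents do not support that inference:

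- No such event is reported.
- The first scheduled thyroid test on combination treatment is at Cycle 4 Day 1, after the DLT window closes at the planned Cycle 3 Day 1.
- SAP Section 6 records dose finding as complete with only DL1 tested.
- SAP 6.6.1.4 tabulates avelumab discontinuations by preferred term, so such stops would be visible.

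This is a clarification worth making for patient management. It is not a threat to the trial's conclusions.

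**What to change.** Add to the Grade 2 paragraph of 5.3.5.8:

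> Grade 1–2 endocrinopathies managed per Table 7 with hormone replacement are exempt from the avelumab hold and the 28-day stop. For Grade 2 liver-test elevation the shorter Table 7 limit applies (beyond 5 to 7 days, manage as Grade 3–4). The 28-day limit remains the outer limit for all other overlapping Grade 2 irAEs, including diarrhea.

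Do not add a general rule that Table 7 overrides the paragraph. No change to the axitinib instructions is requested.

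The cost is a short insertion in a protocol amendment and a note to sites, with no new procedures, visits or patients. The trade-off is explicit: avelumab continues in hormone-replaced Grade 1–2 endocrinopathy, and the stricter of the two limits is kept for the liver.

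### After a first overlapping Grade 3 immune-related diarrhea, Protocol Section 5.3.5.8 stops avelumab for good while the Table 7 it points to resumes it, and nothing says which prevails

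*Protocol*

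**What the plan says.** Protocol Section 5.3.5.8 opens by sending irAE treatment to Table 7. It then warns that some irAEs "may overlap with axitinib toxicities (eg, diarrhea, elevated liver function tests") and gives two paragraphs for such overlapping events.

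- **Overlapping Grade 3 or higher.** The site is to "hold axitinib and follow the specific guidance in Table 7 for avelumab". Once the event is back to Grade 1 or less, the site is to "restart therapy with axitinib at reduced dose level. Avelumab should be permanently discontinued". The last sentence has no exception for a first Grade 3 event.
- **Overlapping Grade 2.** Both drugs are held and the site is to "follow the specific management recommendations described in Table 7". The paragraph then sets its own permanent stop for avelumab: an event unresolved "after holding avelumab for 2 treatment cycles (up to 28 days"), or one that "recurs after re-introduction of avelumab, permanently discontinue avelumab therapy".

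For gastrointestinal irAEs at Grade 3 to 4, Table 7 says "Withhold avelumab for Grade 3. Permanently discontinue avelumab for Grade 4 or recurrent Grade 3". Its follow-up column has avelumab resumed after a steroid taper of at least 1 month when the event was an initial Grade 3.

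**The concern.** A site treating a first Grade 3 diarrhea that it considers immune-related and overlapping cannot obey both texts. One permits re-exposure to avelumab after recovery and the other forbids it. If the stricter rule was intended, a site following Table 7 rechallenges a patient who should not receive the drug again. If Table 7 was intended, a site following the closing sentence permanently withdraws a study drug the patient could have resumed. Either is an error for that patient.

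The choice also feeds the safety tables. SAP Sections 6.6.1.4 and 6.6.4 count related TEAEs and irAEs leading to avelumab discontinuation, and those counts depend on which text a site applied.

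**Working it through.** No arithmetic applies. The check sets the texts side by side.

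**1. The certain case.** Take a first Grade 3 diarrhea, judged immune-related and overlapping, that resolves to Grade 1 or less.

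| Step | Section 5.3.5.8, closing sentence | Table 7, gastrointestinal Grade 3 to 4 |
|---|---|---|
| At onset | avelumab stopped | avelumab withheld |
| After recovery and taper | permanently off | resumed |

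The texts agree at onset and exclude each other at rechallenge.

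**2. Is there a ranking?** Three places could supply one.
- The opening of Section 5.3.5.8 points to Table 7 in general terms. It does not set the table above the overlap paragraphs.
- A later sentence sends suspected irAEs to the guidance in the section as a whole, which contains both rules.
- The irAE row of Table 5 cites Section 5.3.5.8 and Table 7 together, unranked.

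None settles it.

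**3. Which other Table 7 rows are touched?**
- *Conflict only if the event is judged overlapping:* Grade 3 colitis (same row as diarrhea, but not named as overlapping in the section), first Grade 3 rash, Grade 3 creatinine increase, Grade 3 or 4 endocrinopathy, and a first Grade 3 event under other irAEs. Each row allows avelumab to resume. The Protocol Summary and Sections 1.2.3 and 1.3 list fatigue, nausea/diarrhea and hypothyroidism as expected overlaps, but Section 5.3.5.8 does not say that this list defines its term.
- *No conflict:* Grade 4 diarrhea, recurrent Grade 3 diarrhea, and Grade 3 to 4 liver test elevation (the section's other named example). Table 7 stops avelumab permanently in all of these.

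**4. When does the divergence bite?** Table 7 allows resumption only after recovery and a taper of at least 1 month. The DLT window (Protocol Section 3.1.2) is 4 weeks from the first avelumab dose. For an event starting inside that window, a rechallenge would normally come after it closes. Up to then avelumab is off under either text.

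**The case against.** The best defence is that the overlap paragraph is the more specific rule. It was written for this combination and a narrower class of event, and it ends with an unqualified instruction. The Grade 2 paragraph is built the same way: it cites Table 7 and then adds a permanent stop that the matching Table 7 row does not state, since that row says only "If persists >5-7 days or recurs: Treat as Grade 3 or 4". On this reading Table 7 supplies treatment and monitoring, and the paragraph decides whether avelumab returns. The axitinib instruction in Table 5 for Grade 3 to 4 irAEs also matches the overlap paragraph.

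This makes the stricter reading plausible, but it does not make it the written rule. The Grade 3 paragraph refers to Table 7 specifically for avelumab, and the row it leads to contains an instruction to resume avelumab. Nothing limits the reference to managing the event.

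The second defence is the safeguards. Protocol Section 5.3.5.3 requires consultation with the medical monitor for every Grade 3 or 4 drug-related toxicity and before a patient is discontinued. The taper leaves time for that. The last rows of Table 7 also stop avelumab for irAEs persisting 12 weeks and for steroid need beyond 12 weeks, which narrows the group that could be rechallenged. All of this stands, and it lowers the risk of sites diverging. But the monitor reads the same two texts, so consultation does not supply the missing rule.

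**Conclusion.** The inconsistency is real and should be fixed. It is a drafting conflict in a safety stopping rule; neither rule is criticised as a design. The certain case is one: a first Grade 3 diarrhea judged both immune-related and overlapping. The remaining rows depend on how a site applies the word overlapping. The documents do not allow the number of affected patients to be derived.

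Three stronger readings are tempting and are not supported:

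- **That every Table 7 row resuming avelumab after Grade 3 contradicts the section.** Only diarrhea and liver test elevations are named as examples, and the liver rows agree.
- **That DLT counts or the choice of RP2D are distorted.** The timing above argues against the first. On the second, Protocol Section 3.4 does give attention to discontinuations for treatment-related, especially immune-related, events, but nothing shows that the choice would change. SAP Section 6 records that dose finding is complete with DL1 the only combination dose tested.
- **That a formal analysis is at risk.** SAP Section 5.1.1 plans no hypothesis testing. The exposure is individual rechallenge decisions and some variation in descriptive discontinuation counts.

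**What to change.** Make the two texts agree. Unless the sponsor confirms that Table 7 governs, keep the stricter rule:

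- State in Section 5.3.5.8 that, for overlapping irAEs of Grade 3 or higher, permanent discontinuation of avelumab overrides Table 7.
- Limit that paragraph's reference to Table 7 to treatment and monitoring of the event.
- Add the exception to the gastrointestinal Grade 3 to 4 row.

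If the sponsor confirms that Table 7 governs, replace the paragraph's last sentence with: *Avelumab should be permanently discontinued where Table 7 requires it; otherwise withhold and resume per Table 7.*

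In either case it would help to say which events count as overlapping, in particular whether hypothyroidism does, because the conditional rows turn on that.

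The cost is a short protocol amendment with prospective IRB/EC approval (Protocol Section 12.1) and a letter to sites. No extra patients, data or analyses are needed.
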